9.2 Visit Windows

Days are calculated from Day 0, which is the date of the Baseline assessments, randomization, and IP administration.

Screening may be conducted up to 7 days before Baseline (Day 0) in the window Day -7 to Day -1. All post-Baseline visits should be conducted on the specified day, whenever possible. However, when needed, the windows for each visit are:

- ± 1 day window for the Day 7 phone call,
- ± 2 -day window for the Day 14 visit,
- -2 days and +4 days for the Day 28 visit,
- ± 2 day window for the Day 42 visit,
- ± 7 day window for the Week 12 phone call and Week 16 visit.

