11.2.3 Prohibited Medications

The Investigator will inform subjects of the following prohibited medications which may interfere with efficacy evaluations by masking the effect of treatment:

- subjects must not receive treatment with any scabicide, including permethrin, ivermectin, benzyl benzoate, sulfur, lindane, crotamiton, malathion, tea tree oil, or spinosad, between Screening and Day 28. Note that this includes the use of ivermectin for any approved or unapproved indication.
- subjects must not use topical over the counter or prescription medications used to manage itching (i.e., containing corticosteroids, ferric oxide, crotamiton, calamine etc.) between Day 0 and Day 28.
- subjects must also be advised to avoid contact with any treatments taken by their close personal contacts.

Pruritus management outlined in Section 11.2.2 should be actively followed. However, although scabicides are prohibited medications prior to the Day 28 visit, subject wellbeing is the priority. As this is a single dose treatment study, withdrawing from treatment is not applicable. If scabicides are required for the subject's wellbeing, the subject does not need to withdraw from the study for the Investigator to provide scabicides and subjects should continue on-study if they receive scabicides prior to Day 28 (Section 14). An excessive rate of scabicide administration prior to Day 28 can render the study difficult to interpret. The exposure to scabicides prior to Day 28 will be considered a major protocol deviation and subjects will be considered non-responders for the primary analysis (Section 15.6.8).

11.3 After Day 28

If subjects are positive for scabies mites by microscopy or dermoscopy at Day 28, or their clinical presentation has significantly worsened from Day 0, the subject will be given treatment with a scabicide. In the United States, permethrin 5% cream or spinosad 0.9% lotion should be used according to labelled instructions. In other regions such as Latin America, approved standard of care therapy per local guidelines may be used.

In addition to emollients and over-the-counter antihistamines, subjects may use topical over the counter or prescription medications used to manage itching (i.e., containing corticosteroids, ferric oxide, crotamiton, calamine etc.) after Day 28.

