6 STUDY ENDPOINTS

6.1 Primary Efficacy Endpoint

The primary efficacy endpoint is the proportion of index subjects achieving Complete Cure at Day 28. Complete Cure is defined as demonstration of both:

(1) Clinical cure (all signs and symptoms have completely resolved, including burrows, inflammatory/noninflammatory lesions and pruritus).

and

(2) Microscopic or dermatoscopic cure demonstrating the absence of mites, eggs, and/or scybala, and negative dermoscopy for burrows.

Complete Cure will be derived from the individual assessments captured on the Day 28 Scabies Assessment eCRF page where:

- Lesion count is 0, and,
- Pruritus is ‘Absent’, and,
- Mites are ‘Absent’, and,
- Eggs are ‘Absent’, and,
- Scybala are ‘Absent’, and,
- Burrows (by dermoscopy) are ‘Absent’.

An index subject will be considered as having achieved Complete Cure at Day 28 if all of the 6 components are either 0 or “Absent” as specified above. If any of the 6 components are missing, whether because the individual component is missed or because the Day 28 visit was missed, the Complete Cure endpoint at Day 28 will be considered missing and the subject will be imputed as a non-responder (not cured). An exception will be made if the missed visit is non-informative. See Section 9.11.2 for further detail on handling missing data for the Day 28 Complete Cure endpoint.

The Day 28 Complete Cure endpoint for subjects exposed to scabicides prior to their Day 28 assessment will also be imputed as a non-responder (not cured). Scabicides are defined as any scabicide, including permethrin, ivermectin, benzyl benzoate, sulfur, lindane, crotamiton, malathion, tea tree oil, or spinosad used between Day 0 and Day 28. Scabicides do not include products used to manage the symptoms of scabies. Subjects exposed to scabicides as concomitant medications with unknown start dates will also be imputed as non-responders, unless the end date is known and after Day 28.

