9.4.2 Adverse Events and Prior and Concomitant Medications

Dates will not be imputed for Adverse Events or Medical History events. The sites were responsible for imputing start and end dates for TEAEs.

Prior and concomitant medications may have unknown start or end dates. The site makes the determination of whether the medication is a prior or concomitant medication when they enter the medication onto the Prior Medication or Concomitant Medication eCRF page. Partial or unknown dates are not imputed.

Medications entered into the Prior Medication eCRF page with a partial or unknown stop date will be analyzed as both prior and concomitant medications, unless the stop date is a month and/or year combination prior to the study drug administration date.

Subjects exposed to concomitant medications that are scabicides with unknown start dates will be imputed as non-responders, unless the end date of administration is known and is after Day 28.

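### The SAP's exception for scabicides with an unknown start date tests the end date, which cannot show that use began after the Day 28 assessment

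*SAP*

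**What the plan says.** **General rule.** SAP 6.1 states that "subjects exposed to scabicides prior to their Day 28 assessment will also be imputed as a non-responder (not cured"). SAP 9.11.2 has the same cut-off, the assessment.

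**Unknown start date.** Under SAP 6.1, subjects whose concomitant scabicide has no known start date "will also be imputed as non-responders, unless the end date is known and after Day 28". SAP 9.4.2 words the exception as "unless the end date of administration is known and is after Day 28", and SAP 9.11.2 repeats it. SAP 9.4.2 also says that incomplete medication dates are not filled in. The exception speaks only of unknown start dates; partial ones are not addressed.

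**Definition.** SAP 6.1 and SAP 7 list the scabicides, ending with "crotamiton, malathion, tea tree oil, or spinosad used between Day 0 and Day 28", and SAP 6.1 then adds: "Scabicides do not include products used to manage the symptoms of scabies". Protocol 15.6.2 defines rescue medication with the same list and the same exclusion.

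**Visit window.** Protocol 9.2 allows minus "2 days and +4 days for the Day 28 visit".

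**Itch products.** Protocol 11.2.3 prohibits crotamiton twice: once in its list of scabicides, and once among topical itch medications "containing corticosteroids, ferric oxide, crotamiton, calamine etc".

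**The concern.** For an unknown start date the default is non-response, which is conservative. The exception reverses it on evidence that does not bear on the question. What matters is whether the scabicide was used before the assessment. The exception asks instead when use stopped.

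The outcome is the primary endpoint, and the estimand in SAP 3.4 is cure without rescue. A subject wrongly exempted keeps the observed Day 28 result. If that result is clear, the subject enters the primary analysis as an ordinary observed responder. The tipping-point analysis in SAP 9.11.3.2 changes only placebo subjects who were imputed as non-responders, so it never reaches such a subject. The per-protocol set may exclude some of them through the deviation review, but only as a sensitivity analysis.

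**Working it through.** **1. What an end date can show.** Let s be the day of first use, e the day of last use, and A the day of the subject's Day 28 assessment. The window puts A between Day 26 (28 − 2) and Day 32 (28 + 4). Use before the assessment means s < A. The exception knows only that e > 28. Since s ≤ e, that leaves s anywhere up to e. It does not give s ≥ A. An end date before A would prove exposure, but a late end date disproves nothing.

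**2. Whether the pattern can arise.** Protocol 5.2 describes second doses 7 to 14 days after the first. Assume that a course is entered as one record and that A = 28. With a 14-day gap, any start on Days 15 to 27 gives an end after Day 28 (15 + 14 = 29). With a 7-day gap, so does any start on Days 22 to 27 (22 + 7 = 29). All these courses begin before the assessment and meet the exception if the start is recorded as unknown.

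**3. What must coincide.** The start is unknown, the end is known and after Day 28, use did precede the assessment, and all six components are zero or absent. A subject with a component missing for an informative reason is a non-responder anyway.

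**4. The plan's own figure.** Inputs from SAP 4: n = 50 per arm, 40% against 70%, two-tailed alpha 0.019, pooled Z-test.

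- SE under the null = √(2 × 0.55 × 0.45 / 50) = 0.0995
- SE under the alternative = √((0.40 × 0.60 + 0.70 × 0.30) / 50) = 0.0949
- Power = Φ((0.30 − 2.3455 × 0.0995) / 0.0949) = 75.9%, against the stated 75%

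**5. Effect of m misclassified subjects.** Each raises an arm's rate by 1/50 = 2 points. Protocol 5.4.2 derives the 40% placebo rate with scabicide exposure counted as failure, so the m subjects come on top of it. The documents give no rescue rate and no rate of unknown dates, so m is an assumed range.

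| m | Power, m in placebo | Apparent power, m in one moxidectin arm | Chance of a false win, both arms truly 40%, m in moxidectin |
|---|---|---|---|
| 0 | 75.9% | 75.9% | 0.95% |
| 1 | 69.0% | 82.3% | 1.6% |
| 2 | 61.4% | 87.7% | 2.6% |
| 3 | 53.5% | 91.9% | 4.1% |

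**6. Effect on single results.** With z = (p1 − p0) / √(2p̄(1 − p̄)/50), where p̄ is the pooled rate, the two-tailed p-values are:

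| Moxidectin cured | Placebo 20/50 | 21/50 | 22/50 | 23/50 |
|---|---|---|---|---|
| 32/50 | 0.0163 | 0.0275 | 0.0448 | 0.0704 |
| 33/50 | 0.0092 | 0.0161 | 0.0270 | 0.0440 |
| 35/50 (planned) | 0.0026 | 0.0048 | 0.0086 | 0.0150 |

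One subject changes the conclusion at 32/50 and two do at 33/50. At the planned rates three do not. The pooled Z-test is the plan's sample-size and fallback test; the primary test is region-standardized with a bootstrapped standard error, so these p-values are approximate.

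**7. The cut-off wordings side by side.**

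- SAP 6.1 and 9.11.2, imputation rule: exposure before the assessment.
- SAP 6.1 and 7, definition: "used between Day 0 and Day 28".
- SAP 3.4 (Table 1) and 8.5: exposure before Day 28.

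If Day 28 means the visit, these agree. If it means the calendar day, they differ for any assessment not held on Day 28.

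**The case against.** The strongest reply is that the exception is narrow and guarded. It qualifies only the added rule for unknown starts; where other evidence shows use before the assessment, the general rule still applies. Concomitant medication is recorded at Days 7, 14 and 28, which helps to bound a start date. Scabicide use before Day 28 is a major protocol deviation, and SAP 9.11.2 has rescue use determined before the blind break. The exception was probably meant for standard-of-care treatment given after the Day 28 visit. All of this stands, and it keeps the expected number small. But the blinded review has no written rule for these cases, and the rule that is written exempts them.

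Three stronger readings are tempting, and the documents do not support them.

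- **Scabicide use on Days 29 to 31 before a Day 32 assessment is ignored.** The imputation rule itself runs to the subject's assessment, and SAP 7 says that references to a study day mean the protocol's visits. SAP 7 also computes event days from dates, so the wordings need aligning, but no text tells a programmer to ignore such use.
- **Crotamiton use lets a rescued subject count as cured.** It is named as a scabicide and prohibited before Day 28 in both lists of Protocol 11.2.3, and a named item would ordinarily be read as prevailing over a general exclusion. That precedence is unwritten, so this is a conflict to reconcile, not a shown error.
- **The flaw favors one side.** More rescue on placebo is a plausible inference, but the documents give no figure. If true, it would work against moxidectin by raising the placebo rate; misclassification in a moxidectin arm would work the other way.

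**Conclusion.** The end-date exception is wrong as a test and should be replaced. As written, it can leave a subject who was rescued before assessment as a responder in the primary analysis, contrary to the estimand, and no planned analysis has a rule that corrects this.

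The size is small. The number affected is unknown and may be zero, and each subject is worth 2 percentage points in one arm. That can decide a comparison close to 0.019; at the planned 40% and 70% it would take more than three placebo subjects. These figures assume 50 per arm, the pooled Z-test, and misclassified subjects who are clear on all six components.

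The differing cut-off phrases and the double listing of crotamiton are wording conflicts to settle in the same edit. On crotamiton the passages must be reconciled by the sponsor; no view is taken here on its clinical use.

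**What to change.** 1. In SAP 6.1, 9.4.2 and 9.11.2, replace the end-date exception: an unknown or partial start date is non-response unless records show that first use was on or after the subject's actual Day 28 assessment.
2. In SAP 3.4 (Table 1), 6.1, 7, 8.5 and 9.11.2, use one cut-off: any use from Day 0 until the subject's actual Day 28 assessment. Key it to use, not to a start date on or after Day 0, because SAP 7 lets a concomitant medication begin before dosing. State that treatment given at the visit after the assessment counts as after it.
3. Reconcile the passages that name crotamiton as a scabicide (SAP 6.1 and 7, Protocol 15.6.2) with those that list it among itch products (Protocol synopsis and 11.2.3) and with the exclusion of symptom products. State before unblinding which governs the analysis.

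The cost is a few SAP sentences and blinded date queries before the Day 42 lock. The downside is that a subject treated only after the assessment, whose start date cannot be recovered, is counted as a failure. Scabicide treatment after Day 28 is planned for subjects who are mite-positive or significantly worse, so most of them already fail Complete Cure.

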6.2 Secondary Efficacy Endpoints

There are no secondary efficacy endpoints.

6.3 Exploratory Endpoints

Exploratory endpoints will include but are not limited to, for each of the four treatment groups:

- **The proportion of index subjects demonstrating Clinical Cure without microscopic or dermatoscopic cure at Day 28**

Clinical Cure is defined as the demonstration that all signs and symptoms have completely resolved, including burrows, inflammatory/noninflammatory lesions and pruritus. Clinical cure will be derived from the individual assessments captured on the Day 28 Scabies Assessment eCRF page where:

- Lesion count is 0, and,
- Pruritus is ‘Absent’, and,
- Burrows (by dermoscopy) are ‘Absent’.

There will be no imputation for this endpoint except for subjects exposed to scabicides prior to their Day 28 assessment, who will be imputed as a non-responder (not cured). The denominator for the proportion will be subjects in each treatment group with a non-missing data point for this assessment.

- **The proportion of index subjects demonstrating Microscopic or Dermatoscopic cure without clinical cure at Day 28**

Microscopic or Dermatoscopic Cure is defined as the demonstration of the absence of mites, eggs, and/or scybala, and negative dermoscopy for burrows. Microscopic or dermatoscopic cure will be derived from the individual assessments captured on the Day 28 Scabies Assessment eCRF page where:

- Mites are ‘Absent’, and,
- Eggs are ‘Absent’, and,
- Scybala are ‘Absent’, and,

- Burrows (by dermoscopy) are ‘Absent’.

There will be no imputation for this endpoint except for subjects exposed to scabicides prior to their Day 28 assessment, who will be imputed as a non-responder (not cured). The denominator for the proportion will be subjects in each treatment group with a non-missing data point for this assessment.

- **The proportion of index subjects in each of the three categories of cure assessed by the Investigator at Day 28 (Investigator Assessed Cure)**

The *Investigator Assessed Cure* corresponds to the Investigator selection of one of the three categories below that best describes the cure status of the subject at Day 28:

1. The scabies infestation is clear with all signs resolved,
2. The scabies infestation is clear with incomplete resolution of signs, and no additional treatment with standard of care is warranted,
3. The scabies infestation is not clear and additional treatment with standard of care is warranted.

There will be no imputation for this endpoint except for subjects exposed to scabicides prior to their Day 28 assessment, who will be imputed as a non-responder (not cured). The denominator for the proportion will be subjects in each treatment group with a non-missing data point for this assessment.

- **The proportion of index subjects with concordant and discordant Day 28 cure rates, as assessed by the Investigator, and the Complete Cure rate**

For this analysis, an index subject will be considered cured under the Investigator Assessed Cure if either the first or the second category of the assessment is selected. A subject will be considered as not achieving the Investigator Assessed Cure if the third category is selected.

Concordance between Complete Cure and Investigator Assessed Cure will be defined as achieving cure status for both the primary efficacy Complete Cure endpoint and the Investigator Assessed Cure, or not achieving Cure status by both endpoints. Discordance will be defined as not achieving the same outcome by both endpoints.

There will be no imputation for either the Complete Cure or Investigator Assessed Cure endpoints, or any of the components of the Complete Cure endpoint, except for subjects exposed to scabicides prior to their Day 28 assessment, who will be imputed as a non-responder (not cured). The denominator for the proportion will be subjects in each treatment group with a non-missing data point for both of the Complete Cure and Investigator Assessed Cure.

- **The mean and median change from Baseline for index subjects in the total number of lesions to Day 28.**

The change will be calculated as the total number of lesions at Day 28 minus the count at Baseline for each subject.

There will be no imputation for this endpoint, and only subjects in each treatment group with a non-missing data point for both assessments (Day 0 and Day 28) will be included in the change from Baseline. The exception will be subjects exposed to scabicides prior

to their Day 28 assessment, who will have their Day 0 assessment carried forward to the Day 28 assessment for the purposes of calculating change from Baseline.

- **The proportion of index subjects with secondary bacterial skin infections at Day 28**

This endpoint is derived from the secondary bacterial infection assessment captured on the Day 28 Scabies Assessment eCRF page where:

- Secondary bacterial infection is “Present”.

There will be no imputation for this endpoint. The denominator for the proportion will be subjects in each treatment group with a non-missing data point for this assessment, with subjects exposed to scabicides prior to their Day 28 assessment excluded from the analysis.

- **Plasma concentrations of moxidectin in a subset of index subjects selected for sparse PK sampling**

Approximately 20 subjects from each of the moxidectin cohorts (but not placebo) will be selected for sparse PK sampling. Moxidectin plasma concentrations will be determined at four time points, e.g., Day 0 (3- and 10-hours post-dose), Day 28, and Day 42. No pre-dose sample will be collected. Missing plasma concentrations will not be imputed.

- **The proportion of index subjects demonstrating all features of Complete Cure without regard to pruritus**

This endpoint is similar in definition as the primary efficacy Complete Cure endpoint except the pruritus component is not included in the definition, e.g.,:

- (1) Clinical cure (all signs and symptoms have completely resolved, including burrows and inflammatory/noninflammatory lesions).

and

- (2) Microscopic or dermatoscopic cure demonstrating the absence of mites, eggs, and/or scybala, and negative dermoscopy for burrows.

This will be derived from the individual assessments captured on the Day 28 Scabies Assessment eCRF page where:

- Lesion count is 0, and,
- Pruritus is ‘Present’ or ‘Absent’, and,
- Mites are ‘Absent’, and,
- Eggs are ‘Absent’, and,
- Scybala are ‘Absent’, and,
- Burrows (by dermoscopy) are ‘Absent’.

There will be no imputation for this endpoint except for subjects exposed to scabicides prior to their Day 28 assessment, who will be imputed as a non-responder (not cured). The denominator for the proportion will be subjects in each treatment group with a non-missing data point for this assessment.

- **The proportion of index subjects achieving clearance for each individual component of the Complete Cure endpoint**

This endpoint will examine each of the assessments captured on the Day 28 Scabies Assessment eCRF page individually. Subjects may be included in more than one component.

- Lesion count is 0, or,
- Pruritus is 'Absent', or,
- Mites are 'Absent', or,
- Eggs are 'Absent', or,
- Scybala are 'Absent', or,
- Burrows (by dermoscopy) are 'Absent'.

There will be no imputation for this endpoint except for subjects exposed to scabicides prior to their Day 28 assessment, who will be imputed as a non-responder (not cured) for each individual component. The denominator for the proportion will be subjects in each treatment group with a non-missing data point for this assessment.

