6.2.3 Exploratory Endpoints

The exploratory endpoints include but are not limited to:

- The proportion of index subjects demonstrating clinical cure without microscopic or dermatoscopic cure at Day 28.
- The proportion of index subjects demonstrating microscopic or dermatoscopic cure without clinical cure at Day 28.
- The proportion of index subjects demonstrating cure as assessed by the Investigator at Day 28.
- The proportion of index subjects with concordant and discordant Day 28 cure rates as assessed by the Investigator and the Complete Cure rate.
- The change from Baseline for index subjects in the total number of lesions at Day 28.
- The proportion of index subjects with secondary bacterial skin infections at Day 28.
- Plasma concentrations of moxidectin in a subset of index subjects selected for sparse PK sampling.

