9.11.5.1 Proportion of Subjects Reporting Day 28 Cure Rates

For FAS subjects, summary statistics for the exploratory endpoints listed below by randomized treatment group and overall will be provided. The definitions of each of the variations of cure endpoint are provided in Section 6.3. There will be no adjustment for region:

- Complete Cure, (n, % FAS)
- Clinical Cure, (n, % FAS)
- Microscopic or Dermatoscopic Cure, (n, % FAS)
- Complete Cure without regard to pruritus (n, % FAS)
- Investigator Assessed Cure:
 - The scabies infestation is clear with all signs resolved, (n, % FAS)
 - The scabies infestation is clear with incomplete resolution of signs, and no additional treatment with standard of care is warranted, (n, % FAS)
 - The scabies infestation is not clear and additional treatment with standard of care is warranted, (n, % FAS)

Along with the number and percent (proportion), the 95% CIs intervals for each treatment group and overall will also be provided. For each of the endpoints, the missing data and imputation methods are outlined under Section 6.3. In general, no imputation will be conducted except for subjects exposed to scabicides. The analysis will be conducted using the FAS.

Additionally, the table will be repeated with stratification by region, summarized by randomized treatment group and overall.

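### Two exploratory endpoints named as one cure without the other are derived in SAP 6.3 as marginal cure rates, so headings and derivations disagree and the named endpoints are not tabulated

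*SAP*

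**What the plan says.** Protocol 6.2.3 lists two exploratory endpoints, "The proportion of index subjects demonstrating clinical cure without microscopic or dermatoscopic cure at Day 28" and "The proportion of index subjects demonstrating microscopic or dermatoscopic cure without clinical cure at Day 28". The synopsis and Protocol 15.5.3 repeat them. SAP 6.3 keeps both as headings: "The proportion of index subjects demonstrating Clinical Cure without microscopic or dermatoscopic cure at Day 28" and "The proportion of index subjects demonstrating Microscopic or Dermatoscopic cure without clinical cure at Day 28".

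The text under each heading defines something else.

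- First endpoint: "Clinical Cure is defined as the demonstration that all signs and symptoms have completely resolved, including burrows, inflammatory/noninflammatory lesions and pruritus". Then "Clinical cure will be derived from the individual assessments captured on the Day 28 Scabies Assessment eCRF page where" three conditions hold: lesion count 0, pruritus absent, burrows absent.
- Second endpoint: "Microscopic or Dermatoscopic Cure is defined as the demonstration of the absence of mites, eggs, and/or scybala, and negative dermoscopy for burrows". Four conditions are listed: mites, eggs, scybala and burrows all absent.

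For both, the only imputation is that subjects exposed to scabicides before Day 28 are set to not cured, and the denominator is subjects with non-missing data.

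SAP 9.11.5.1 refers back to 6.3 for its definitions and specifies the row "Clinical Cure, (n, % FAS" and a matching row for Microscopic or Dermatoscopic Cure. Neither row carries the *without* condition. The exploratory objectives (Protocol 6.1.3, SAP 3.3) ask for clinical cure rates and for combined microscopic and dermatoscopic cure rates, also without that condition. SAP 1.2, which lists the departures from the protocol, does not mention these endpoints.

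**The concern.** As named, each endpoint is a discordance: cured on one criterion and not on the other. As derived, each is the overall rate of one cure. Complete Cure requires all six components to be clear, so a subject with Complete Cure meets both derivations, which is the opposite of what the headings describe.

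The discordant groups matter for interpretation here. The protocol background and section 11.2.2 say that itch can persist four to six weeks after effective treatment (the background adds skin lesions), and section 5.4.3 treats 28 days as a minimum for all signs and symptoms to resolve. Subjects free of mites but not yet clinically clear are therefore the group one would look at to understand why Complete Cure was missed.

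There is also a procedural consequence. SAP 1.1 says that the SAP supersedes the protocol's statistical methods where they differ, and that analyses not defined in advance are labelled post hoc. Left as it stands, two endpoints named in the protocol drop out without explanation, or come back only as post hoc results.

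**Working it through.** **The plan's own figure.** The documents state no expected value for the exploratory endpoints. The planning Complete Cure rates in SAP 4 (Protocol 15.2.1) are used below for sizing, so the power attached to them was reproduced first: 40% against 70%, 50 per arm, pooled-variance Z test, two-tailed alpha 0.019.

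- Null SE = √(2 × 0.55 × 0.45 / 50) = 0.0995
- Alternative SE = √((0.40 × 0.60 + 0.70 × 0.30) / 50) = 0.0949
- Power = Φ((0.30 − 2.345 × 0.0995) / 0.0949) = 75.9%, against a stated figure of about 75%. It reproduces.

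**Which subjects each rule accepts.** Code the six components (lesions, pruritus, mites, eggs, scybala, burrows) as clear or not clear. There are 2⁶ = 64 patterns.

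| Rule | Required clear | Patterns accepted |
|---|---|---|
| Clinical Cure, as derived | lesions, pruritus, burrows | 2³ = 8 |
| Clinical Cure and not Microscopic/Dermatoscopic Cure, as named | the same, with at least one of mites, eggs, scybala present | 7 |
| Microscopic/Dermatoscopic Cure, as derived | mites, eggs, scybala, burrows | 2² = 4 |
| Microscopic/Dermatoscopic Cure and not Clinical Cure, as named | the same, with a lesion or pruritus present | 3 |

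In each pair the one extra pattern is all six clear, which is Complete Cure. So for subjects with all six components observed:

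P(as derived) = P(as named) + P(Complete Cure).

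**Size at the planning rates.**

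| Arm | Complete Cure | Excess of derived over named | Named can be at most | Derived is at least | Smallest ratio |
|---|---|---|---|---|---|
| Moxidectin | 70% (35/50) | 70 points | 30% | 70% | 100/30 = 3.33 |
| Placebo | 40% (20/50) | 40 points | 60% | 40% | 100/60 = 1.67 |

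For illustration, assume 2% (1 of 50) are clinically cured but not mite-free. This figure is an assumption, not from the documents. The derivation would then give 36/50 = 72% on moxidectin and 21/50 = 42% on placebo.

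The plan assumes 40% or less on placebo, so the excess there may be smaller: 20, 10 or 5 points if placebo Complete Cure is 20%, 10% or 5%.

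**Is the discordance computed elsewhere?** No. The 2x2 table in SAP 9.11.5.2 sets Complete Cure against Investigator Assessed Cure. The component endpoint in 6.3 gives clearance of single items, from which joint outcomes cannot be recovered.

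**The case against.** The best defence is that almost everything else in the plan agrees with the derivations. The objectives ask for marginal rates, the definitions table in SAP 7 is marginal, and the rows in 9.11.5.1 are correctly labelled for what is computed. A reader might infer that the output will present marginal rates under a discordance title. The documents do not support that: the specified row labels are right, and the final table shells are in a separate document.

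A reader might also infer that the discordant information is lost. With all six components observed it is not. Complete Cure is the intersection of the two cures and sits in the same table, so each discordant count is the marginal count minus the Complete Cure count. This stands, with a limit. A subject clear of lesions, pruritus and burrows but with a missing scybala result counts in Clinical Cure and has no observed Complete Cure status, so subtraction would wrongly call that subject discordant. The denominators do not help: 6.3 uses non-missing subjects, while 9.11.5.1 writes percentages of the FAS.

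The SAP also adds Complete Cure without the pruritus component. That shows part of the mirror group (those held back by itch alone), but not those with residual lesions, and nothing on the first endpoint.

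Finally, *without* might have been meant as *without regard to*, which would make the derivations the intended ones. The same section uses the longer phrase for pruritus and spells it out as either present or absent, so this reading is weak. Even if it is right, the headings need correcting.

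**Conclusion.** The point holds as an inconsistency between named and derived endpoints. In SAP 6.3 the two headings and their derivations describe different quantities, the two discordant endpoints named in the protocol are not tabulated, and SAP 1.2 does not list the change.

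The gap is exactly the arm's Complete Cure rate when all components are observed: 70 points on moxidectin and up to 40 on placebo at the planning rates. One might conclude that the derived proportion is far too large in every arm. That is secure for moxidectin at the planning rate but not for placebo, where the gap shrinks with the true Complete Cure rate.

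Only descriptive exploratory summaries are affected. The primary endpoint, its analysis, alpha and power do not depend on these definitions. The correction is worth making because it is cheap and can be made before unblinding.

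**What to change.** Keep the marginal Clinical Cure and Microscopic or Dermatoscopic Cure rates, under those names, for the stated objectives. Add one descriptive 2x2 table per arm crossing the two cures. Its off-diagonal cells are the two endpoints the protocol names: Clinical Cure and not Microscopic/Dermatoscopic Cure, and the reverse.

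Two rules must be stated with it:

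- Denominator: subjects with all six components observed. This also calls for reconciling the denominators in 6.3 and 9.11.5.1.
- Scabicide exposure before Day 28: not cured on both criteria, so counted in neither discordant cell. The present non-responder rule is ambiguous for an outcome that means cured on one criterion and not on the other. The text should also say whether exposed subjects with an incomplete Day 28 assessment enter the table.

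If only marginal rates are intended, rename the two headings in 6.3 and list the change from Protocol 6.2.3 and 15.5.3 in SAP 1.2.

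The cost is one table and a few sentences of SAP text. No new data are needed, since all six components are already on the Day 28 Scabies Assessment page.
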